5.6. Additional Devices or Procedures

There may be circumstances requiring the use of other techniques (mechanical thrombectomy devices or medical therapy) should the SOFIA[™] / SOFIA[™] PLUS Catheter fail to achieve recanalization in the targeted vessel. **After three (3) unsuccessful aspiration attempts the investigator must** use other techniques. However, the investigator **may decide at any point** to change his/her treatment for optimum patient care. Any devices which are CE-Mark approved for mechanical thrombectomy might be used. Use of these devices after the first aspiration using the SOFIA[™] / SOFIA[™] PLUS Catheter will not be considered a protocol deviation but will be recorded.

5.7. Angiographic Imaging

At pre-procedure Digital Subtraction Angiography (DSA) shall be performed to define the angioarchitecture of the occluded vascular segment. When possible, an assessment of collateral blood flow by DSA should be done per institutional standard of care, particularly in cases of terminal internal carotid artery occlusion. Prior to mechanical thrombectomy by the Sofia Device, baseline Thrombolysis in Cerebral Infarction (TICI) scores shall be obtained by DSA. CTA or MRA is not an acceptable substitute for this assessment. The Investigator shall make an initial assessment of TICI flow in the target vessel territory. TICI scores are to be assessed after completion of the procedure during the final angiographic run. Pre-procedure and post-procedure (pseudonymized) angiograms shall be sent to an independent Core Laboratory to make a final determination on TICI flow.

5.8. Follow-up at 24 ± 12 Hours Post-procedure

Per institutional standard of care at the site, follow-up imaging (MRI preferred, CT if medically required) shall be performed for all patients at 24 (-12/+12) hours post-stroke to assess

for intracranial hemorrhage and for infarct volume assessment by the Core Lab based on ECASS definitions [25]:

- HI 1 (small petechiae along the margins of the infarcted area without space-occupying effect)
- HI 2 (more confluent petechiae within the infarcted area but without space-occupying effect)
- PH 1 (hematoma in \leq 30% of the infarcted area with some slight space-occupying effect)
- PH 2 (hematoma in > 30% of infarcted area with substantial space-occupying effect).

A physical exam, as well as clinical and neurological assessments, will be completed per institutional standard of care at 24 (-12/+12) hours post treatment. Data to be collected and then captured on eCRFs include:

- Any adverse events or serious adverse events
- Vital signs (blood pressure and heart rate)
- Significant findings from clinical assessment and physical exam (i.e. all new, worsening, or improved conditions)
- All significant neurological findings, NIHSS and mRS Score (24 (-12/+12) hours), collected during independent neurological assessment by qualified personnel

5.9. Follow-up at Discharge (7±3Days Post-procedure)

Per routine practice at the site, patients will be evaluated for neurological (NIHSS) and disability (mRS) status

- All significant neurological findings, NIHSS and mRS Score
- Any adverse events and serious adverse events will be reported by the site

5.10. Follow-up at 90 ± 14 Days Post-procedure

- Per routine practice at the site, patients will be evaluated for their functional outcome with mRS
- A Quality of Life questionnaire will be conducted with the patient or relative
- Any adverse events and serious adverse events will be reported by the site
- Antiplatelet therapy regimen is recorded throughout the study
- The "Study Completion Form" CRF will be filled in at the end of the study (even if the patient is lost to follow-up before the 90-day assessment, withdrew his or her consent, or is deceased)

5.11. Unscheduled Visits

As per site routine practice, patient safety and study assessments (imaging, NIHSS, mRS) at other follow-up visits should be done as clinically indicated with corresponding data documented in the source documents and appropriate CRFs.

5.12. Termination of Patient Participation

All patients have the right to terminate their participation at any point during the study. In addition, Principal Investigators also have the ability to terminate patient participation in the study. Reasons for termination include: completion of study, patient withdrawal, physician-directed patient withdrawal, lost-to-follow-up, and death. A description of the reason for their termination will be documented in the patient's medical file and in the appropriate study Case Report Forms (CRF).

Withdrawal:

A participant or his/ her legal authorized representative can stop the participant's participation in this study by withdrawing consent, or decide to discontinue participation if the participant is no longer able to participate in the study (owing, concomitant disease or administrative reasons). If a participant or his/ her legal authorized representative decides to withdraw the participant from the study, it can be done at any time. Whenever possible, the reason for discontinuation should be recorded in the source documentation and on the eCRF. Withdrawing consent will not result in any penalty whatsoever for the participant. Further treatment will be performed according to local practice. The data of the participant who withdraws his/her informed consent, collected prior to withdrawal, will not be discarded, and will be used in the final analysis of the study. Lost to follow-up:

After three documented attempts to reach the participant by telephone have failed, a certified letter will be sent to the participant. The participant will be considered lost to follow-up if this communication is unsuccessful.

Participants who discontinue study participation prematurely will not be replaced.

6 Assessment of Safety and Effectiveness

6.1. Safety

Safety will be assessed by collecting adverse event (AEs) data during the endovascular procedure, at 24 hours post-procedure, at hospital discharge or 7-10 days, and at 90 days after the index procedure.

Adverse events will be ascertained by the investigators using non-leading questions, noted as spontaneously reported by the patients to the medical staff or observed during any measure-

ments on all study days. The observation period begins with start of the endovascular pro-cedure and ends at follow- up at day 90. AEs are also documented at the unscheduled visits, if applicable.

6.1.1. Device Deficiency

A device deficiency is defined as inadequacy of a medical device with respect to its identity, quality, durability, reliability, safety, or performance. Device deficiencies include malfunctions, use errors, and inadequate labeling. All device deficiencies must be reported to the Study Coordinator, the device manufacturer, and, if necessary, the respective site's government agencies.

If a device deficiency results in an adverse event for the patient, this adverse event (AE) will be considered reportable and must be reported as an adverse event in the eCRF; in case of seriousness also on the SAE-form (see 6.1.2). Device deficiencies that do not result in an adverse event for the patient do not need to be recorded as an AE, as they are not considered an AE. They will be considered as technical event and documented separately.

6.1.2. Adverse Events and Serious Adverse Events

Definition Adverse Event (AE):

Any untoward medical occurrence, unintended disease or injury, or any untoward clinical signs (including an abnormal laboratory finding) in subjects, users or other persons whether or not related to the medical device.

Definition Serious Adverse Event (SAE):

Any event meeting the following criteria will be classified as SAE according to the GCP and ISO 14155 definition:

a) Led to a death,

b) Led to a serious deterioration in health that resulted in:

1) a life-threatening illness or injury, or

2) a permanent impairment of a body structure or a body function, or

3) patient hospitalization or prolongation of existing hospitalization, or medical or surgical in-tervention to prevent life threatening illness or injury or permanent impairment to a body structure or a body function.

4) medical or surgical intervention to prevent life-threatening illness or injury or permanent impairment to a body structure or a body function,

c) Led to fetal distress, fetal death or a congenital abnormality or birth defect.

NOTE 1: This includes device deficiencies that might have led to a serious AE (SAE) if suitable action had not been taken, intervention had not been made, or circumstances had been less fortunate. These are handled under the SAE reporting system. NOTE 2: A planned hospitalization for pre-existing condition, or a procedure required by the Clinical Investigation Plan, without a serious deterioration in health, is not considered to be an SAE.

This registry study is designed to minimize potential risks to the participants. However, the following events associated with endovascular treatment / thrombectomy should be documented on the eCRF.

Table 3:	Events
----------	--------

Event	Collected data
Intracranial hemorrhage (symptomatic	Date/time; Symptomatic/asymptomatic
/asymptomatic)	
New disabling ischemic stroke (NIHSS in-	Date/time; Inside/outside the region of the
crease of at least 4 points)	treated vessel /assignment not possible
New non-disabling ischemic stroke (If	Date/time; Inside/outside the region of the
NIHSS increase it should be less than 4	treated vessel /assignment not possible
points)	
Severe extracerebral hemorrhage (i.e. re-	Date/time;Gastrointestinal/local (groin) /
quiring surgical treatment or transfusion)	other
Myocardial infarction	Date/time
Pseudoaneurysm femoral artery	Date/time
TIA	Date/time; Inside/outside the region of the
	treated vessel /assignment not possible
Death	Date/time

5.1.3. Reporting of SAEs Incidentsby the Investigator to the Sponsor

All SAEs must be reported by the investigator [to the responsible Safety Officer at the KKS Heidelberg] within 24 hours after the SAE becomes known using the "Serious Adverse Event" form. The reporting will be performed by faxing a completed 'SAE Form' to the KKS Heidelberg, [contact]

All SAEs incidents will be reported to the national competent authorities, to the ethics committees and other administrative bodies according to the national regulatory requirements by the Safety Officer at the KKS Heidelberg.

6.2. Effectiveness

The effectiveness of the device will be assessed based on angiographic revascularization of the occluded target vessel immediately post-procedure as defined by a TICI 2b or 3 score and at 90 days after the procedure as defined by good functional outcome with a mRS score of o-2.

6.2.1. Functional Outcome

Good patient functional outcome at 90 day follow-up will be defined by a mRS score of 0-2.

6.2.2. Angiographic Outcome

Angiographic revascularization of the occluded target vessel immediately post-procedure as defined by a TICI 2b or 3 score assessed by an imaging corelab

Grade o	No perfusion or anterograde flow beyond site of occlusion
Grade 1	Penetration but not perfusion. Contrast penetration exists past the initial of struction but with minimal filling of the normal territory
Grade 2	Incomplete perfusion wherein the contrast passes the occlusion and opa fies the distal arterial bed but rate of entry or clearance from the bed is slower incomplete when compared to non-involved territories
Grade 2A	Some perfusion with distal branch filling of <50% of territory visualized
Grade 2B	Substantial perfusion with distal branch filling of \geq 50% of territory visualiz
Grade 2C	Near complete perfusion except for slow flow/occlusion in 1 or 2 branches few distal cortical vessels, or presence of small distal cortical emboli
Grade 3	Complete perfusion with normal filling of all distal branches

 Table 4 - Thrombolysis in Cerebral Infarction (TICI) Perfusion Categories**

** From Almekhlafi et al. Interv Neuroradiol. 2014 Jan-Feb;20(1):21-7. Epub 2014 Feb 10.

The Investigator shall make an initial assessment of TICI flow in the target vessel territory. Preprocedure and post-procedure pseudonymized angiograms shall be sent to an independent Core Laboratory to make a final determination on TICI flow.

6.3. Risk/Benefit Analysis

The risks associated with the Sofia/Sofia Plus Catheter as an adjunct to IV rtPA are similar to those associated with cerebral angiography and with other intra-arterial methods of recanalization.

6.3.1. Angiography

An angiographic procedure requires that a catheter be placed into the body, and in this case, threaded through the body to the neurovasculature. Once the catheter is in the proper position, contrast media is infused through the catheter to examine the vessels. Patients may encounter bleeding from vessel perforation, vessel spasm, swelling, or bruising at the access site where the catheters are placed in the body (usually the groin area). Additionally, once the catheter reaches the neurovasculature, there is a chance that the catheter could cause bleeding, hematoma, vessel thrombosis, dissection, distal embolization, pseudoaneurysm, and arteriovenous fistula formation. Patients who are allergic to contrast media are at further risk and may experience a reaction that may include hives, itching, nausea, or breathing difficulty. Contrast media may also cause kidney damage in some patients. The above risks of angiography are well known and generally unlikely to occur. However, if any of the above risks occur and are severe enough, patient death is possible.

6.3.2. Computed Tomography Scan (CT Scan) and Magnetic Resonance Imaging (MRI)

The risks encountered during a CT scan are low. The risks mentioned above for contrast media allergy are possible with a CT scan. There is also a slight risk of injury from being exposed to the radiation associated with a CT scan; however, the levels of radiation, and the risks associated with radiation exposure are low. MRI does not use ionizing radiation. There are no known harmful side-effects associated with temporary exposure to the strong magnetic field used by MRI scanners. These exams are performed according to usual routine practice at the site, for such stroke patients admitted and treated accordingly.

6.3.3. Thrombectomy/Embolectomy

The risks of intra-arterial thrombectomy/embolectomy are similar to those associated with existing intra-arterial methods of recanalization. These risks include:

- allergic reaction and anaphylaxis from contrast media
- acute occlusion
- hematoma or hemorrhage at access site
- infection
- inability to completely remove thrombus
- air embolism

- arteriovenous fistula
- ischemia
- kidney damage from contrast media
- death
- neurological deficits including stroke
- device malfunction
- distal embolization
- intracranial hemorrhage
- vessel spasm, thrombosis, dissection
- false aneurysm formation

Risks directly associated with the Sofia/Sofia Plus Catheters are similar to the above. Considerable testing has been completed to ensure that the Sofia/Sofia Plus Catheters do not pose a significant risk. Testing includes both in vitro and in vivo testing. In addition, the following will be performed to minimize the risks:

• As per usual site practice, patients will be carefully evaluated before entering the study to ensure that the location of the occlusion and the time of stroke onset are appropriate for treatment with the Sofia/Sofia Plus Catheters.

• During the clinical study, the procedure will be performed in an Operating Room or in an angiographic suite with an Operating Room standby. Therefore, should complications arise requiring surgery or other interventions, the surgery or intervention can be initiated without delay. All sites will be carefully selected to ensure that either a stroke unit operating according to national stroke guidelines or a physician experienced in treating patients presenting with acute ischemic stroke is available.

• Patients will be carefully monitored as per site routine practice and the follow-up period. The Investigator will examine and perform various diagnostic tests before, during, and after the procedure, at 7-10 days or at hospital discharge and at 90 days (±14 days) after the procedure. Use of the Sofia/Sofia Plus Catheters offer several potential benefits, which may include a higher success rate of recanalization with an acceptable device-related serious adverse rate. Based on the above information, the benefits of the Sofia/Sofia Plus Catheters outweigh the potential risks associated with their clinical use.

7 Imaging Core Lab

For all study participants, the imaging core laboratory will perform the qualitative and semiquantitative assessments of vessel occlusion (site of occlusion, length of occlusion, TICI score) and ASPECT score at baseline and follow-up as well as revascularization at the end of the procedure (TICI score). Furthermore, ICH and infarct volume assessment at 24 (-/+ 12) hours using clinical routine data will be performed. All sites must provide the complete routine imaging (as per local standard of care), and all images must be de-identified prior to submission (pseudonymisa-tion). A detailed imaging core lab manual will be provided.

8 Data Management

Clinical site personnel will enter data into eCRFs in the EDC system provided by the Study Coordinator for study data collection. The Study Coordinator or designee will be responsible for confirming the overall integrity of the data. The image data workflow will be described more extensively in the imaging core lab manual.

8.1. Data Prottection

The data obtained in the course of the trial will be treated pursuant to the EU Data Protection Regulation (EU Datenschutz-Grundverordnung (DSGVO)).

During the clinical trial, patients will be identified solely by means of their individual identification code (patient number). Trial findings stored on a computer will be stored in accordance with local data protection law and will be handled in strictest confidence. For protection of these data, organizational procedures are implemented to prevent distribution of data to unauthorized persons. The appropriate regulations of local data legislation will be fulfilled in its entirety.

The patient consents in writing to release the investigator from his/her professional discretion in so far as to allow inspection of original data for monitoring purposes by health authorities and authorized persons (inspectors, monitors, auditors). Authorized persons (clinical monitors, auditors, inspectors) may inspect the patient-related data collected during the trial ensuring the data protection law.

The investigator will maintain a patient identification list (patient numbers with the corresponding patient names) to enable records to be identified.

Patients who did not consent to circulate their pseudonymized data will not be included into the trial.

This protocol, the eCRFs and other trial-related documents and material must be handled with strict confidentiality and not be disclosed to third parties except with the express prior consent of Sponsor. Staffs of the investigators involved in this study are also bound by this agreement.

9 Statistical Methods

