	tients suffering an Acute Ischemic Stroke when assessed at 24 hours, dis-			
	charge and 90 days after treatment.			
Sample Size & Duration	250 patients will be enrolled. All patients will be followed for 90 days or			
of Study:	until death.			
Number of Sites:	Up to 20 European sites (France, Germany, Austria, Italy, Netherlands)			
Allocation:	Non-randomised, single arm			
Patient Population:	Patients who are at least 18 years of age presenting with an acute ischem-			
	ic event in the anterior cerebral circulation that can be treated within 6			
	hours from AIS symptom onset. Those eligible to be treated with SOFIA™/			
	SOFIA™ PLUS will be enrolled after having signed an informed consent			
	form (or having one signed on his or her behalf by a legally authorized			

	representative or an independent physician).				
Patient Selection Crite- ria: Target Enrollment Peri-	cal and imaging considerations. Patients who meet all of the inclusion criteria and none of the exclusion criteria will be eligible for study partici- pation.				
od & Study Duration:	enrollment of the first patient and end upon enrollment of the last patient into the study. Total study duration is estimated to be up to 45 months (up to 42 months of enrollment + 3 months of follow-up).				
Inclusion Criteria:	 Participant is ≥ 18 Demonstrated occlusion of the distal intracranial carotid artery, middle cerebral artery (M1 or M2) or anterior cerebral artery (A1 or A2) proven by CT and/or MRI 				
	 NIHSS ≥ 2 and ≤ 30 at screening Start of the thrombectomy procedure within 6 hours of the onset of stroke symptoms Pre event mRS ≤1 				
	 5. Pre event firks ≤1 6. Informed consent by the patient, legal guardian, or inclusion of patient under presumptive will after consultation of an independent physician and statement of investigator 				
Exclusion Criteria:	1. Patient is more than 6 hours from symptom onset				
	2. Rapidly improving neurologic examination				
	3. Evidence of cerebral ischemia in the posterior circulation				
	4. Severe unilateral or bilateral carotid artery stenosis requiring stent treat- ment				
	5. Presence of an existing or pre-existing large territory infarction				
	6. Absent femoral pulses				
	7. Excessive vascular tortuosity that will likely result in unstable access				
	8. Pregnancy; if a woman is of child-bearing potential a urine or serum beta HCG test is positive				
	9. Known contrast product allergy				

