4.3. Study Population

Up to 250 consecutive patients at up to 15 centers in Europe with symptoms of acute ischemic stroke who are eligible for inclusion into this study. The patients must meet the following inclusion criteria and none of the exclusion criteria:

Inclusion Criteria:

- Participant is \geq 18
- Demonstrated occlusion of the distal intracranial carotid artery, middle cerebral artery (M1 or M2) or anterior cerebral artery (A1 or A2) in the anterior circulation proven by CT and/or MRI
- NIHSS ≥ 2 and < 30 at screening
- Start of the thrombectomy procedure within 6 hours of the onset of stroke symptoms
- Pre event mRS ≤ 1
- Patient or patient's legally authorized representative or impartial witness/independent physician has received information about data collection and has signed and dated an Informed Consent Form

Exclusion Criteria:

- Patient is more than 6 hours from symptom onset
- Evidence of cerebral ischemia in the posterior circulation
- Rapidly improving neurologic examination
- Severe unilateral or bilateral carotid artery stenosis requiring stent treatment
- Absent femoral pulses
- Presence of an existing or preexisting large territory infarction
- Excessive vascular tortuosity that will likely result in unstable access

- Pregnancy; if a woman is of child-bearing potential and urine or serum beta HCG test is positive
- Known contrast product allergy
- Patient has a severe or fatal comorbidity that will likely prevent improvement or follow-up or that will render the procedure unlikely to benefit the patient
- Evidence of intracranial hemorrhage (SAH, ICH, etc.)

Imaging exclusion criteria:

- Significant mass effect with midline shift or intracranial tumor
- Baseline non-contrast CT or DWI MRI evidence of a moderate/large core defined as extensive early ischemic changes of Alberta Stroke Program Early CT score (ASPECTS) 0-5

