5.2. Informed Consent

Image data acquisition, treatment via interventional procedure with a CE-marked device and clinical evaluation are all considered standard of care and thus there is no need for additional consent. Informed consent for data collection must be obtained prior to enrollment of patients in this study and data transmission.

However, most patients will be unable to give their consent prior to treatment. We expect that approximately 60% of patients will be unable to give informed consent prior to therapy with the SOFIA[™]/ SOFIA[™] PLUS catheter. Excluding this group of patients from the study would entail severe scientific and clinical drawbacks. Results would be biased by systematically excluding more severe strokes and patients with aphasia, i.e. mostly left hemispheric strokes. As a consequence, the generalizability of the study results would be limited.

Once the patient's potential eligibility has been determined, the Investigator will discuss the study and ask the patient, or the patient's legally authorized representative, based on the site routine practice and regulatory requirements, if they are interested in participating in the data collection. The study will be explained to the consenting person in lay terms. Study personnel should document the consent process in the participant's medical record per Good Clinical Practice (GCP). The participant or legally authorized representative is to be provided a copy of the signed ICF. In case the patient was not able to provide his consent before the procedure, all attempts will be made to obtain his consent before discharge. Additionally, patients who signed an Informed Consent Form but did not meet general inclusion/exclusion criteria should also be recorded in the screen failure log.

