Informed consent has to be obtained prior to enrolment of patients in SESAME. In the normal case written consent will be given by the patient after detailed information about the clinical trial by the investigator. The investigator or sub-investigator will explain the study in detail including risks and benefits for the patient, financing of the study and potential conflicts of interest. Furthermore, the investigator will clarify that the patient or his/her legal guardian will document his/her agreement to participate in the SESAME study by signing the informed consent form.

However, given the sample to be studied (i.e. acute stroke patients showing neurological deficits that may comprise aphasia or disturbance of consciousness) we expect that a certain proportion of patients (estimated 60%) will be unable to give informed consent. Excluding this group of patients from the clinical trial would entail severe scientific and clinical drawbacks. Results would be biased by systematically excluding more severe strokes and patients with aphasia, i.e. mostly left hemispheric strokes. As a consequence, the generalizability of the study results would be limited. Strictly speaking, in case of a positive result this could not be transferred to the patients excluded from the trial (e.g. aphasic patients). This large group would still be excluded from this effective treatment.

A possible solution would allow the *enrolment of patients unable to give informed consent* based on their alleged will following pre-specified criteria. These criteria would have to consider a potential individual benefit as well as any possible risk of participation in the clinical trial. In general the protection of the patient and his autonomy has to be weighed against the potential individual benefit as well as the scientific interest. Following European and national regulations the enrolment of patients (temporarily) unable to give informed consent into clinical trials is possible in an emergency situation if a legal guardian is available and – after careful consideration of possible risks and potential individual benefit – a participation in the clinical trial would comply with the patient's presumptive will. Moreover, standard treatment following best medical practice must not be withheld to the patient by enrolment in the clinical trial.

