For patients eligible for enrolment in SESAME best medical practice in these patients usually comprises the use of CT to rule out hemorrhage or prove ischemic infarction followed by an interventional procedure (thrombectomy), hospitalization and monitoring in a specialized stroke unit. Additional standard treatment consists of supervision and modification of physiological parameters (such as blood pressure, body temperature, blood glucose) and early secondary prevention (e.g. Aspirin).

Suggestion for enrolment of patients unable to give informed consent in SESAME:

[figure not shown]
- A Patient is able to give informed consent and able to provide written consent:
 - Patient is informed by investigator, patient information is handed over to the patient, and patient provides written consent. This may occur prior to treatment or after treatment if the patient was unable to give informed consent and underwent standard of care treatment in agreement with the protocol.
- B Patient is unable to give informed consent, legal guardian is available

Legal guardian acts on behalf of the patient; legal guardian is informed by investigator, patient information is handed over to the legal guardian, legal guardian provides written consent

C –Patient is unable to give informed consent; legal guardian is not available, enrolment of patient by consensus between investigator and independent physician

If the patient is unable to give informed consent and no legal guardian has been appointed, the patient may be enrolled by consensus between the investigator and an independent physician about an the presumed will of the patient; if possible, patient's next of kin should be contacted to appraise the patient's presumed will; the decision has to be documented using a special form. Immediately parallel an application for appointing a legal guardian will be started later patient or legal guardian will be informed by the investigator and may or may not provide written consent. Enrolment through the independent physician will be included to minimize selection bias.

Figure 1: "Overview of Ways of Obtaining Informed Consent"

These options for obtaining the informed consent are NOT equal or interchangeable. The highest priority will always be to obtain informed consent by the participant himself. Only if this option is not possible, other ways may be approached.

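### A patient enrolled on presumed will who dies before anyone can be asked to consent is in the cohort under 10.3.1 but, on a literal reading, out under 8.1

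*Protocol*

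**What the plan says.** Four parts of the protocol bring a route C patient into the study.

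- Section 10.3.1, route C, covers a patient who cannot consent and for whom no guardian has been appointed: "the patient may be enrolled by consensus between the investigator and an independent physician". An application for a guardian is started in parallel, and "later patient or legal guardian will be informed by the investigator and may or may not provide written consent". The purpose is stated: "Enrolment through the independent physician will be included to minimize selection bias".
- Inclusion criterion 6 in the synopsis accepts a "patient under presumptive will after consultation of an independent physician and statement of investigator".
- The matching criterion in 4.3 begins "Patient or patient's legally authorized representative or impartial witness/independent physician has received information about data collection" and goes on to require a signed form, so an independent physician may sign.
- Section 5.4 sets enrolment at catheter insertion, and 9.2.1 defines the ITT sample as all enrolled participants.

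Four passages point the other way or do not fit.

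- Section 8.1: "Patients who did not consent to circulate their pseudonymized data will not be included into the trial".
- Section 5.2 requires consent for data collection before enrolment and data transmission. It tells the investigator to "ask the patient, or the patient's legally authorized representative, based on the site routine practice and regulatory requirements", with no mention of an independent physician.
- Section 10.3.1 also says that data collection does not begin before consent, although data may be captured retrospectively.
- The regulatory background in 10.3.1 says that enrolling a patient who cannot consent "is possible in an emergency situation if a legal guardian is available". Route C exists for the case where none is.

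**The concern.** The protocol gives no rule for a route C patient whose written consent is never obtained because nobody could be asked. One site could keep the patient under 10.3.1 and 9.2.1, and another could drop the patient under 8.1.

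The difference matters because it is tied to the primary outcome. Whether a signature follows depends partly on the patient surviving long enough to be asked, or for a guardian to be appointed. A patient who dies has mRS 6 and cannot count as a success. If such patients leave the denominator, the mRS 0-2 rate rises, and a single-arm registry has no comparator in which a similar loss could offset it. Sections 5.2 and 10.3.1 themselves warn that leaving out patients who cannot consent would bias the results, and route C was added for that reason.

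**Working it through.** **1. Does another rule settle the matter?**

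- The discard rule in 10.3.1 and the retention rule in 5.12 concern consent that was given and then withdrawn. Here none was given or withdrawn.
- The per-protocol definition in 9.2.1 keeps deaths before day 90, but only for patients already in the data set.
- The imputation in 9.2.2 (multiple, worst case, best case) is written for loss to follow-up. It cannot reach a patient whose data were never transmitted.
- Section 5.2 asks sites to seek consent before discharge from patients who could not give it beforehand. It does not say what follows if that is impossible.

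None of these decides the case.

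**2. The plan's own figure.** Section 9.1 states that 236 patients give a half-width of 6.0 points at an expected rate of 32.6%. With the normal approximation:

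n = 1.96² × 0.326 × 0.674 / 0.06² = 234.5, rounded up to 235.

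At n = 236 the half-width is 1.96 × √(0.326 × 0.674 / 236) = 5.98 points. At n = 250 it is 5.81. The sample-size figure is reproduced and is not in question.

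**3. Shift if these patients are left out.** Inputs from the protocol:

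- p = 0.326 (9.1).
- N = 250.
- 60% expected to be unable to consent before treatment (5.2 and 10.3.1), or 0.60 × 250 = 150 patients. This includes those who later consent themselves (route A) and those with a guardian (route B), so it is only a ceiling for route C.

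Inputs that the protocol does not give, taken as assumptions:

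- f, the share of the cohort left out: 2% to 10%.
- pₑ, the mRS 0-2 rate among those left out: 0% (for example, all died) to 20%.

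Expected observed rate = (p − f × pₑ) / (1 − f).

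| f | Patients left out of 250 | pₑ = 20% | pₑ = 10% | pₑ = 0% |
|---|---|---|---|---|
| 2% | 5 | 32.9% (+0.3) | 33.1% (+0.5) | 33.3% (+0.7) |
| 5% | 12.5 | 33.3% (+0.7) | 33.8% (+1.2) | 34.3% (+1.7) |
| 10% | 25 | 34.0% (+1.4) | 35.1% (+2.5) | 36.2% (+3.6) |

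The corners of the range are (0.326 − 0.02 × 0.20) / 0.98 = 0.329 and 0.326 / 0.90 = 0.362. The 25 patients in the last row are one sixth of the 150 expected to be unable to consent. With 225 patients left, the half-width is 6.2 to 6.3 points before any loss to follow-up.

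**4. What a bound would show.** Take f = 10%. The full cohort has 0.326 × 250 = 81.5 expected good outcomes.

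- If none is among the 25 left out, the reported rate is 81.5 / 225 = 36.2%. Counting the 25 as not mRS 0-2 gives 81.5 / 250 = 32.6%.
- If 20% of the 25 (5 patients) had a good outcome, the reported rate is 76.5 / 225 = 34.0% and the bound is 76.5 / 250 = 30.6%.

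The bound therefore equals or lies below the full-cohort rate, as a lower bound should.

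**The case against.** The best defence is that the sections can be read together. The caption of Figure 1 presents all three routes as ways of obtaining consent, and both inclusion lists accept the independent physician. On that view a route C patient has met the consent requirement, and 8.1 is aimed at people who refuse. Taken strictly, 8.1 would even bar route B patients, because it speaks only of the patient's consent and never of a guardian's. That suggests loose general wording and not a rule against route C. This reading is tenable, but nothing in the text states it, and the words in 10.3.1 that leave later consent open do not say what follows.

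Three stronger inferences are tempting, and the documents do not support them.

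- A reader might conclude that every patient who stays incapable is at risk of removal. Route C starts a guardian application at once, so such patients should gain someone who can be asked. The group left over is mainly those who die first, plus those for whom no guardian is appointed in time.
- A reader might take the background sentence in 10.3.1 as allowing enrolment only with a guardian. The word is not there, and the sentence summarises regulation in the course of discussing a possible solution. It fits route C badly but does not define the cohort.
- A reader might treat the bias as demonstrated and always upward. Its direction depends on those left out doing worse than average. That is plausible for a group made up largely of deaths, but it remains an assumption.

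The content of Figure 1 and the special form used for route C are also not available to check.

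**Conclusion.** The point holds in a limited form. The protocol does not say consistently whether a route C patient stays in the cohort when death, or a guardian not appointed in time, prevents anyone from being asked. Sections 4.3, 5.4, 9.2.1 and 10.3.1 and the synopsis put the patient in. Section 8.1, read literally, takes the patient out, and 5.2 and the data-collection sentence in 10.3.1 add to the doubt. The patient's membership of the ITT set is itself inferred from the enrolment wording and the ITT definition, since 10.3.1 does not state it outright.

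Applied literally, 8.1 would remove patients partly by outcome and would defeat the reason given for route C. Under the assumed 2-10% left out and 0-20% good outcomes among them, the upward shift is about 0.3 to 3.6 points, below the planned 6.0-point half-width throughout. The protocol supports no narrower figure. This cannot be left to an analysis plan, because data that were never transmitted cannot be restored at analysis.

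**What to change.** - Reconcile 5.2, 8.1 and the consent text in 10.3.1 (the guardian sentence, route C and the start of data collection). Where national law and the ethics committee allow, state that the exclusion in 8.1 applies to refusal of consent, and not to route C patients who could not be asked. Whether the law allows this in each of the five countries cannot be settled from the protocol.
- Report by count the patients treated with the device but left out of the data set, split into those who refused (in person or through a guardian) and those who could never be asked.
- Where the data of the second group cannot be used, give the primary rate once more with those patients added to the denominator and counted as not mRS 0-2, as a lower bound.

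The cost is an amendment of a few sentences with an ethics and legal check in each country, one extra row in the results, and possibly a slightly lower reported good-outcome rate.
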